5.2.1.3. Cytarabine

Commercially available cytarabine will be used. Refer to the local package insert or Institutional Guidelines for detailed formulation, preparation and dispensing information.

5.2.1.4. Azacitidine

Upon site activation, Pfizer will provide a supply of azacitidine for clinical use. Refer to the local package insert for detailed formulation, preparation and dispensing information.

5.2.2. Preparation and Dispensing

Only qualified personnel who are familiar with procedures that minimize undue exposure to them and to the environment should undertake the preparation, handling, and safe disposal of chemotherapeutic agents.

5.3. Administration

5.3.1. General Guidelines

In the monotherapy cohort, PF-04449913 administered as a single agent will be evaluated. In the combination cohort, three different PF-04449913 combinations (with LDAC for the unfit patient population, with cytarabine/daunorubicin for the fit patient population, and with azacitidine for the azacitidine patient population) will be evaluated. In the Continuation

Cohort, PF-04449913 continuously administered as a single agent will be evaluated for safety. Patients should be instructed to take their medication at approximately the same time each day and to not take more than the prescribed dose at any time.

Study drugs are administered in cycles. Bone marrow evaluations are performed at specified times to determine clinical response and treatment progression decisions within the trial (except for the Continuation Cohort).

5.3.1.1. In the combination cohorts, all patients should be weighed within 72 hours prior to dosing for every cycle to ensure they did not experience either a weight loss or gain >10% from the prior weight used to calculate the amount of cytarabine, daunorubicin required, or azacitidine for dose preparation. Decision to recalculate cytarabine, daunorubicin, or azacitidine dose based on the weight obtained at each cycle can be in accordance with institutional practice for changes in weight of 10% or less; however, if the patient experienced either a weight loss or gain of >10%, the amount of cytarabine, daunorubicin, or azacitidine required for study drug preparation and administration must be recalculated using this most recent weight obtained. Study Treatment Duration in the Monotherapy Cohort

Treatment with PF-04449913 may continue for up to 12 cycles or until disease progression or relapse, patient withdrawal, or unacceptable toxicity occurs (whichever comes first). However, patients who complete 12 cycles of study treatment demonstrating clinical benefit with manageable toxicity, and are willing to continue receiving the study treatment, may be given the opportunity to do so upon agreement between Investigator and Sponsor and pending study drug availability.

5.3.1.2. Study Treatment Duration in the Combination Cohorts

Combination Cohort 1 (Unfit Patients):

Study treatment (LDAC plus PF-04449913) may continue for up to 12 cycles or until disease progression or relapse, patient refusal, or unacceptable toxicity occurs (whichever comes first). However, patients who complete 12 cycles of study treatment, demonstrate clinical benefit with manageable toxicity, and are willing to continue receiving the treatment (monotherapy of PF-04449913 or combination therapy), may be given the opportunity to do so following discussion and agreement between the Investigator and Sponsor, and pending confirmation of study drug availability.

Expansion Cohort of LDAC combination for efficacy (Unfit Patients):

Study treatment (LDAC plus PF-04449913) may continue until disease progression or relapse, patient refusal, or unacceptable toxicity occurs (whichever comes first).

Combination Cohort 2 (Fit Patients):

Study treatment may continue until patient refusal, or the patient develops unacceptable toxicity or demonstrates either resistant disease during induction (ie, the bone marrow blast

count is greater than or equal to the screening bone marrow blast count), or disease progression/relapse after induction but before maintenance (see [Appendix 5](#) and [Appendix 8](#))

- Patients with residual disease following the first induction (ie, persistent leukemia on bone marrow exam [ie, lower blast counts than the screening bone marrow but still >5% blasts and not meeting a complete response]) are candidates for a second cycle of induction if re-induction criteria are met;
- In addition, following completion of the induction and consolidation, PF-04449913 single agent may be given to eligible patients as maintenance treatment for a maximum of 6 cycles. However, patients who complete the maintenance treatment period and who demonstrate clinical benefit with manageable toxicity, and who are willing to continue receiving PF-04449913 single agent, may be given the opportunity to do so following agreement between Investigator and Sponsor, and pending confirmation of study drug availability.

Combination Cohort 3 (Azacitidine Combination):

Since responses to azacitidine may require 4-6 cycles of administration to emerge, treatment with the study drug combination should be continued for at least 6 cycles, or until death, unacceptable toxicity, or patient refusal (whichever is first). If documentation of disease progression occurs within the first 6 cycles of study treatment, the patient **SHOULD NOT** be withdrawn from study treatment following agreement between the Investigator and Sponsor if, in the Investigator's judgment, the patient is still likely to receive clinical benefit.

Treatment with the study drug combination should be continued beyond 6 cycles of treatment until objective disease progression or relapse (unless according to the Investigator there is reasonable evidence of clinical benefit, eg, HI [hematologic improvement], to justify continuation on treatment following agreement between the Investigator and Sponsor), death, unacceptable toxicity, or patient refusal (whichever is first).

5.3.1.3. Study Treatment Duration in the Continuation Cohort (Monotherapy Cohort)

In this cohort, the patient receiving PF-04449913 will continue to receive study treatment until the time of disease progression, unacceptable toxicity, death, withdrawal of consent or termination of the study by Sponsor, whichever comes first. The patient may continue PF-04449913 treatment after objective progression of disease has been determined if the patient continues to experience clinical benefit, in the opinion of the investigator, and following discussion with the Sponsor. Refer to [Appendix 7](#) for the definition of disease progression.

5.3.2. PF-04449913 Administration

PF-04449913 will be administered once daily and orally on a continuous basis for all patients. A cycle is defined as 28 days unless the cycle is prolonged due to toxicity per [Section 5.3.9](#) and [Section 5.3.10](#). PF-04449913 will be administered without adjustment for body size and with plenty of water. Tablets must not be crushed or cut; they must be swallowed whole and not chewed. Patients should be instructed to self-administer their medication in the morning at approximately the same time each day and to not take more

than the prescribed dose at any time. The patient will be reminded not to take their dose at home on clinic days but to bring their bottle into clinic so that PF-04449913 may be administered as described in the schedule of activities.

If a patient misses a day's dose entirely, they must be instructed not to "make it up" the next day. If a patient vomits anytime after taking a dose, they must be instructed not to "make it up," but to resume subsequent doses the next day as prescribed. If a patient inadvertently takes 1 extra dose during a day, the patient should not take the next dose of PF-04449913.

If the in-clinic study visits cannot be conducted due to COVID-19-related reasons, arrangements to send investigational product and dosing diary to patient's home via the third courier may be implemented. Participants must provide verbal consent for providing the contact details for shipping purposes. The verbal consent should be documented in the source document. Tracking record including temperature logs of shipments (eg. Lot number, receipt record by the participant and/or study drug status at the time of receipt, etc.) and the chain of custody of the study medication must be kept in the Investigational Product Accountability Log (IPAL) and/or the participant's medical records.

Patients should return all unused or partially used bottles of investigational product and dosing diaries at the next in-clinic visit.

5.3.3. PF-04449913 in Combination with LDAC (Combination Cohort 1 and Expansion Cohort of LDAC combination for efficacy: Unfit Patients)

[figure not shown]
- PF-04449913 will be commenced on Day 3 of Cycle 1 for PK assessment purposes (for Combination Cohort 1) or Day 1 of Cycle 1 (for Expansion Cohort) and thereafter given once daily and continuously for 28-day cycles (starting on Day 1 for all other cycles);
- PF-04449913 will be administered in the morning at approximately the same time as the first LDAC subcutaneous injection on days these agents are dosed together. On days that PF-04449913 is dosed alone, PF-04449913 will be administered in the morning at approximately the same time each day;
- LDAC will be given at a dose of 20 mg (not adjusted for the patients weight) subcutaneously (SC) twice daily (morning and evening; approximately 12 hrs apart) on Days 1-10 days of the 28 day cycles.
- If the in-clinic study visits cannot be conducted due to COVID-19-related reasons, LDAC administration may be skipped only once. In such case, the safety assessments should be performed by phone or video contact, and/or by utilizing the test results from a local clinic if applicable. If 2 or more consecutive skips are required, the investigator and the Sponsor should have a consultation to determine the necessity of the study treatment discontinuation.

5.3.4. PF-04449913 in Combination with Cytarabine/Daunorubicin (Combination Cohort 2: Fit Patients)

In this cohort, treatment consists of 3 distinct phases: induction, consolidation and maintenance. All patients must meet specific criteria to enter each phase and will be required to wait the full 28 days of each cycle before progressing (Figure 4). The only exception is for receiving the second cycle of induction which, if needed, can occur as early as Day 21 of induction Cycle 1.

Patients may require placement of a central venous catheter prior to initiation of therapy per institutional guidelines.

Figure 4. Overview of Combination Cohort 2 (Fit Patients) Treatment Plan

5.3.4.1. Induction

Patients will participate in their first induction therapy for a total of 28 days. However, if a patient requires a second cycle of induction therapy due to residual leukemia or investigator

opinion, this second course may start as soon as possible following the Cycle 1/Day 21 bone marrow evaluation. If the induction cycle(s) extends longer than 28 days, dosing with PF-04449913 should continue daily in the absence of PF-04449913-related toxicity that would prevent dosing.

The intensive chemotherapy doses will be unaltered for both induction cycles regardless of toxicity or response (see Section 5.3.1 for dose adjustments based on body weight changes). For the first induction cycle only, PF-04449913 will be started on Day -3 and will then be given once daily and continuously for the duration of the treatment. Daunorubicin will be given on Days 1 through 3 once daily at a dose of 60 mg/m²/day by IV together with cytarabine on Days 1 through 7 at a dose of 100 mg/m²/day by continuous intravenous infusion (CIV). Where possible, daunorubicin should be given as close as possible to the administration of PF-04449913. Daunorubicin and cytarabine should be administered per institutional guidelines.

The second induction cycle may be delayed up to an additional 28 days from Day 28 of the previous cycle to allow the patient to recover from any severe reversible hematologic or non-hematologic drug related toxicity. Treatment with PF-04449913 should continue during any delay before the start of the second cycle of induction in the absence of significant PF-04449913-related toxicity that would prevent dosing. The second cycle of induction should not be performed if the patient has clinically significant cardiotoxicity (LVEF <45%) and in this case the patient should be discontinued from treatment.

The bone marrow may be repeated at the Investigator's discretion as required for clinical staging at any time prior to the next cycle of chemotherapy.

The following rules apply for progression from induction to consolidation (Figure 5):

- Patients who successfully obtain a **CR** or **CRi** after induction are eligible to enter the consolidation phase of the trial 28 days from the start of the last induction cycle;
- Patients with **residual leukemia** at the end of induction Cycle 1 may be treated with a second cycle of induction therapy. If after the second cycle of induction the patient still shows signs of residual or resistant leukemia, they must be discontinued from treatment and followed as described in Section 5.3.7;
- Patients with **resistant leukemia** after the first and/or second course of induction will be discontinued from treatment and followed as described in Section 5.3.7.

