5.3.8. Food Requirements

In all study cohorts, only in Cycle 1 PF-04449913 will be administered with plenty of water on an empty stomach ie, patients should refrain from food and beverages (except for water) where possible for at least two hours before and two hours after dosing throughout treatment administration. From Cycle 2 onwards, PF-04449913 can be administered with or without food. In the Expansion Cohort of LDAC combination for efficacy and Continuation Cohort, PF-04449913 may be administered with or without food in Cycle 1 and thereafter.

5.3.9. Recommended Dose Modifications [Monotherapy Cohort, Combination Cohort 1 and Expansion Cohort (Unfit Patients), Combination Cohort 2 (Fit Patients) and Continuation Cohort (Monotherapy Cohort)]

Every effort should be made to administer the study treatments at the planned dose and schedule.

In the event of study treatment related toxicity, dosing may be delayed and/or dose reduced as described below in [Table 13](#). In the event of multiple toxicities, dose modification should

be based on the worst toxicity observed. Patients are to be instructed to notify Investigators at the first occurrence of any adverse symptom.

Dose modifications may occur in three ways:

1. Within a cycle: dose interruption/reduction until adequate recovery during a given treatment cycle.
 - **PF-04449913 (All Cohorts):**
 - Doses of PF-04449913 that are held or missed during any cycle due to PF-04449913-related toxicities will not be made up (eg. cycles will not be prolonged beyond the 28th calendar day in order to make up any missed PF-04449913 doses during the cycle);
 - PF-04449913 may be dose reduced during any cycle. However, for patients who are enrolled into the 25 mg dose level in the monotherapy cohort, PF-04449913 dose reduction is not allowed.
 - **Backbone chemotherapy (Combination Cohort 1, Expansion Cohort and Combination Cohort 2 only):**
 - No dose-reductions are permitted in Cycle 1 for any of the backbone chemotherapeutic agents;
 - After Cycle 1, if a toxicity is attributed to the backbone chemotherapy and not to PF-04449913, chemotherapeutics may be delayed or reduced (see [Table 13](#) and [Table 15](#)) (while PF-04449913 dosing should be continued);
 - Missed doses of backbone chemotherapy (LDAC, cytarabine/daunorubicin) can be made up if the Investigator considers it appropriate according to standard practice.

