2. Between cycles: next cycle administration may be postponed due to toxicity in the previous cycle.
 - A cycle may be extended to a maximum of 56 days for non-hematologic toxicity, or to a maximum of 70 days if due to hematologic toxicity. PF-04449913 dosing should continue if observed toxicity is not deemed related to PF-04449913;
 - If a treatment interruption continues beyond Day 28 of the current cycle for any agent, then the day when full treatment (all agents in the combination) is restarted will be counted as Day 1 of the next cycle for all agents.
3. In the next cycle: dose reduction based on worst toxicity in the previous cycle.

For all drug combinations:

A study treatment related continuous treatment interruption or delay of >28 days for non-hematologic toxicity OR >42 days for prolonged myelosuppression defined as ANC <500/ μ L or platelet count <10 x10⁹/L in a normal bone marrow with <5% blasts and no evidence of disease or dysplasia, will result in permanent discontinuation from treatment, unless the patient is demonstrating clinical benefit as agreed by the Investigator and Sponsor (Table 13).

Table 13. Recommended Dose Modification Criteria for Treatment-Related Toxicity [Monotherapy Cohort, Combination Cohort 1 and Expansion Cohort (Unfit Patients), Combination Cohort 2 (Fit Patients) and Continuation Cohort (Monotherapy Cohort)]

Drug	Toxicity	Grade 1	Grade 2	Grade 3	Grade 4
PF-04449913	Non Hematologic	Continue at the same dose level.	Continue at the same dose level. If persistent (at least 7 days) and not responding to optimal medical management, withhold dose until toxicity is grade ≤ 1 , then resume treatment at the same dose level or reduce the dose by 1 level at the discretion of the investigator.	Withhold dose until toxicity is grade ≤ 1 , or has returned to baseline, then resume treatment at the same dose level or reduce the dose by 1 level at the discretion of the investigator. (Nausea, vomiting or diarrhea must persist at Grade 3 or 4 despite maximal medical therapy to require dose modification).	Withhold dose until toxicity is grade ≤ 1 , or has returned to baseline, then reduce the dose by 1 level and resume treatment, or discontinue at the discretion of the investigator. (Nausea, vomiting or diarrhea must persist at Grade 3 or 4 despite maximal medical therapy to require dose modification).

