LDAC	Delay of more than 28 days for non-hematologic toxicity	Discontinue treatment			
Induction Cytarabine/Daunorubicin	Non Hematologic and Hematologic ≤ 42 days	No dose modification permitted for either agent.			
Induction Cytarabine/Daunorubicin	Hematologic - prolonged myelosuppression lasting > 42 days	If ANC $< 500/\mu\text{L}$ or platelet count $< 10 \times 10^9/\text{L}$ in a normal bone marrow with $< 5\%$ blasts and no evidence of disease or dysplasia for > 42 days, discontinue treatment			
Induction Cytarabine/Daunorubicin	Delay of more than 28 days for non-hematologic toxicity	Discontinue treatment			

Drug	Toxicity	Grade 1	Grade 2	Grade 3	Grade 4
Consolidation Cytarabine	Non Hematologic	Continue at the same dose level.	Continue at the same dose level.	Withhold dose until toxicity is grade ≤ 1 , or has returned to baseline, then resume treatment at the same dose level or reduce the dose by 1 level at the discretion of the investigator (Nausea, vomiting or diarrhea must persist at Grade 3 or 4 despite maximal medical therapy to require dose modification).	Withhold dose until toxicity is grade ≤ 1 , or has returned to baseline, then reduce the dose by 1 level and resume treatment, or discontinue at the discretion of the investigator. (Nausea, vomiting or diarrhea must persist at Grade 3 or 4 despite maximal medical therapy to require dose modification).
Consolidation Cytarabine	Hematologic - prolonged myelosuppression lasting >42 days	If ANC $<500/\mu\text{L}$ or platelet count $<10 \times 10^9/\text{L}$ in a normal bone marrow with $<5\%$ blasts and no evidence of disease or dysplasia for >42 days , discontinue treatment			
Consolidation Cytarabine	Hematologic - myelosuppression lasting ≤ 42 days	If ANC $<500/\mu\text{L}$ or platelet count $<10 \times 10^9/\text{L}$ for ≤ 42 days in a normal bone marrow with $<5\%$ blasts and no evidence of disease or dysplasia, withhold dose until toxicity is grade ≤ 2 , or has returned to baseline, then resume treatment at same dose level or reduce the dose by 1 level and resume treatment, or discontinue at the discretion of the investigator.			
Consolidation Cytarabine	Delay of more than 28 days for non-hematologic toxicity	Discontinue treatment			

5.3.9.1. Additional Guidance for Intra-Patient Dose Modification [Monotherapy Cohort, Combination Cohort 1 and Expansion Cohort (Unfit Patients), Combination Cohort 2 (Fit Patients) and Continuation Cohort (Monotherapy Cohort)]

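### Combination Cohort 2: Sections 5.3.4.1 and 5.3.9 of the protocol give different maximum delays before a second induction cycle when the toxicity is hematologic (Day 56 against Day 70)

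*Protocol*

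**What the plan says.** Protocol Section 5.3.4.1 (Induction) is written for Combination Cohort 2. On the second course it states: "The second induction cycle may be delayed up to an additional 28 days from Day 28 of the previous cycle". The purpose given is "to allow the patient to recover from any severe reversible hematologic or non-hematologic drug related toxicity". There is one limit, and it covers both kinds of toxicity.

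Protocol Section 5.3.9 sets dose-modification rules for several cohorts and lists Combination Cohort 2 among them: "5.3.9. Recommended Dose Modifications [Monotherapy Cohort, Combination Cohort 1 and Expansion Cohort (Unfit Patients), Combination Cohort 2 (Fit Patients) and Continuation Cohort (Monotherapy Cohort". Its between-cycles item reads: "A cycle may be extended to a maximum of 56 days for non-hematologic toxicity, or to a maximum of 70 days if due to hematologic". So there are two limits, split by type of toxicity.

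Protocol Section 5.3.2 defines a cycle as 28 days unless it is prolonged for toxicity, and refers to Sections 5.3.9 and 5.3.10 for that prolongation. Section 5.3.4.1 does not mention Section 5.3.9 when it sets its own limit. No sentence exempts the second induction from Section 5.3.9 or says which section prevails.

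**The concern.** Both passages set a maximum for the same interval, the time from the start of the first induction cycle to the start of the second. They give the same answer for non-hematologic toxicity and different answers for hematologic toxicity. If a patient's counts recover late enough, a site reading Section 5.3.4.1 would conclude that the window for re-induction has closed. A site reading Section 5.3.9 would conclude that it is still open. Two sites could treat identical patients differently and each claim to follow the protocol.

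What is at stake is whether a second daunorubicin/cytarabine course may start in that window and, if it does, whether it is recorded as a deviation. SAP Section 5.6 requires all deviations to be described in the study report, so the classification needs a single rule.

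**Working it through.** The protocol states the limits in two forms: a delay counted from Day 28 in Section 5.3.4.1, and a total cycle length in Section 5.3.9. Put on one scale:

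**Inputs**
- Standard cycle: 28 days (Protocol 5.3.2).
- Delay allowed before second induction, any toxicity: 28 days after Day 28 (Protocol 5.3.4.1).
- Maximum cycle length: 56 days non-hematologic, 70 days hematologic (Protocol 5.3.9, between cycles).

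**Reproducing the figures in Section 5.3.9**
- Non-hematologic: 28 + 28 = 56 days.
- Hematologic: 28 + 42 = 70 days.

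**Comparison**

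| Toxicity | Section 5.3.4.1 | Section 5.3.9 | Difference |
|---|---|---|---|
| Non-hematologic | 28 + 28 = Day 56 | Day 56 | 0 days |
| Hematologic | 28 + 28 = Day 56 | Day 70 | 70 − 56 = 14 days |

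The window of disagreement is Days 57 to 70, for hematologic toxicity only. I read each limit as the last day of the extended cycle. Another day-count convention applied to both sections moves both ends together and leaves the 14 days unchanged.

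**Does anything in the documents settle it?**
- Section 5.3.9 is meant to reach this cohort: its heading names Combination Cohort 2, and Section 5.3.2 sends the reader there for prolonged cycles.
- Section 5.3.4.1 is meant to reach hematologic toxicity: it names it.
- The 70-day sentence carries no condition on marrow status, so it is not confined to patients without residual disease.
- No precedence statement was found.

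**Number of patients.** The cohort has 6 patients (Protocol 3.1.2). Each patient re-induced in the window would be 1/6 = 17% of it. The documents give no basis for estimating how many, if any, that is.

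**The case against.** The strongest reply is that a specific rule sits inside a general ceiling. Section 5.3.4.1 is the only text written for the second induction. Section 5.3.9 is a general between-cycles maximum in a section of recommended modifications that covers several cohorts. Both are worded as permissions, and a site that stays within Day 56 complies with both. On that reading nothing conflicts and only a cross-reference is missing. This has some force, and it may be what was intended. It does not settle the matter, because Section 5.3.2 refers cycle prolongation to Section 5.3.9, that section names this cohort, and nothing exempts re-induction from it. A reader cannot tell whether the single limit in Section 5.3.4.1 is a deliberately stricter rule or an oversight.

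A reader might also infer more than the documents support:

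- **That Table 13 contradicts Section 5.3.4.1 as well.** Its induction row "Hematologic - prolonged myelosuppression lasting > 42 days" is a stopping trigger based on how long myelosuppression lasts in a normal marrow with under 5% blasts. It is not an allowed delay counted from Day 28. Section 5.3.1.2 describes residual-disease candidates for re-induction as having more than 5% blasts, so the row does not fit them, although Section 5.3.4.1 also allows a second course on investigator opinion. The other induction row, "Delay of more than 28 days for non-hematologic toxicity", agrees with the 28 days in Section 5.3.4.1.
- **That the discrepancy decides who comes off treatment.** Section 5.3.4.1 states no consequence for exceeding 28 days. The stopping rule in Section 5.3.9 ("delay of >28 days for non-hematologic toxicity OR >42 days for prolonged myelosuppression defined as ANC" and so on) has an exception for clinical benefit agreed by the investigator and sponsor.
- **That late recovery is the usual case.** The documents do not say so. They expect re-induction early, from Day 21 (Section 5.3.4), as soon as possible after the Day 21 marrow (Section 5.3.4.1).
- **That the primary endpoint or a response estimate is affected.** The DLT period in this cohort ends by Day 28 of the first induction cycle, and the delay criterion for a DLT is non-hematologic only (Section 3.2). SAP Section 8.2.2 gives listings, not rates, for disease status in this cohort.

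**Conclusion.** The inconsistency is real and narrow. For hematologic toxicity, Sections 5.3.4.1 and 5.3.9 disagree for 14 days (Days 57 to 70) on whether a second induction may start, and no precedence is stated. For non-hematologic toxicity they agree.

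This rests on the text of those two sections and on the absence of any sentence that ranks them. It does not depend on Table 13, on how often counts recover late, or on any power or error-rate figure.

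The effect is on whether late re-induction is permitted and how it is classified as a deviation. The exposure and discontinuation tables in the SAP could be touched only if a patient falls in the window. The number is unknown and may be zero. Protocol Section 1.2.8 reports 45 patients already enrolled and treated as of 29 January 2020, against a planned maximum of 49. The remaining effect may therefore be mainly on how past cases are classified.

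**What to change.** Reconcile the delay sentence in Section 5.3.4.1 with the 70-day sentence in Section 5.3.9, or add a sentence stating which section governs the second induction in Combination Cohort 2. The result should be one maximum delay for hematologic toxicity and one for non-hematologic toxicity. The clinical team chooses the value; this review takes no view on which limit is right.

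The cost is one sentence in the protocol. If induction in this cohort is already complete, a clarification note would do, recording which limit is used to classify any re-induction that began on Days 57 to 70. No added data collection, patients or analyses are needed.
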